5.3.2 Secondary Efficacy Endpoints

Overall Survival (OS) related secondary endpoint

The following OS related endpoints are considered as secondary endpoints:

- OS for the MGMT unmethylated group
- OS for the MGMT methylated group
- OS for the *EGFRvIII*-mutated tumor subgroup

Progression Free Survival (PFS) related endpoints

PFS is defined as time from randomization to the date of progression of disease (PD) assessed centrally per Response Assessment in Neuro-Oncology (RANO) criteria or death, whichever occurs first. Any PD or death that occurs > 20 weeks after the previous scan date will be excluded along with the following scans. Subjects without an event will be right-censored at the date of last follow up for disease progression. Patients with no

post baseline follow up for progression and who doesn't experience a death event within 20 weeks after the randomization date will be censored at the day of randomization.

The PFS related secondary endpoints are:

- PFS, assessed by independent central review
- PFS, assessed by independent central review for *EGFRvIII*-mutated tumor subgroup

MDASI-BT symptom severity and interference score

This is a validated PRO instrument used to assess the severity of brain tumor related symptoms and its impact on daily function in last 24 hours. It consists of 22 symptom items and 6 interference items. Each item is rated from 0 to 10, with higher score indicating worse symptoms/interference.

MDASI-BT symptom severity score is defined as average over 13 core symptom items and 9 brain tumor symptom items. The MDASI-BT symptom severity score will be obtained if more than 50% of the items (at least 12 out of 22 items) are completed on a given assessment using the formula: (sum of items answered) \times 22/number of items answered.

MDASI-BT symptom interference score is defined as an average of 6 interference items. The MDASI-BT symptom interference score will be obtained if more than 50% of the items (at least four out of six items) are completed on a given assessment using the formula: (sum of items answered) \times 6/number of items answered.^{18,28}

A change of ≥ 1 point on a 10-point scale at follow-up assessment with respect to baseline will be considered as clinically relevant. Changes in symptom severity score and symptom interference score at each time point will be classified into 3 categories: improved (≤ -1), stable (> -1 and < 1), and deteriorated (≥ 1).

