The secondary endpoints based on this measure are as follows:

- Deterioration Free Survival (i.e., decrease by 1 unit or death, whichever comes first) in MDASI-BT symptom severity score
- Deterioration Free Survival (i.e., decrease by 1 unit or death, whichever comes first) in MDASI-BT symptom interference score

HVLT-R

This standardized neurocognitive function test is used to assess change in verbal memory over time. This test has been validated within brain-disordered population. The HVLT-R Total Recall Score will be computed by summing the total number of words across 3 trials (Trial 1, Trial 2 and Trial 3). Then, the Total Recall Score will be standardized using the published age specific normative data from a healthy population.

A change of ≥ 5 points in raw HVLT-R total recall score with respect to baseline will be considered as clinically relevant. Changes in HVLT-R total recall score at each post-baseline time point will be classified into 3 categories: deteriorated (≤ -5), stable (> -5 and < 5) and improved (≥ 5) (Wefel et al., 2011).

The secondary endpoint based on this measure is:

- Deterioration Free Survival in HVLT-R total recall score.

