5.3.3 Exploratory Efficacy Endpoints

Overall Survival (OS)

- Survival rates at the end of 0.5, 1, 2, 2.5, 3, 4, and 5 years
- OS in non-EGFRvIII subjects

Progression Free Survival (PFS)

- Centrally-assessed PFS rates at the end of 0.5, 1, 2, 2.5, 3, 4, and 5 years

- Centrally-assessed PFS for the MGMT unmethylated and methylated sub-groups
- Centrally-assessed PFS in non-EGFRvIII subjects
- Progression free survival (PFS), assessed by investigator

HRQoL assessments per QLQ-C30 questionnaire developed by EORTC:

The Quality of Life Questionnaire Core 30 (QLQ-C30) is a 30-item patient self-report questionnaire validated for use in a cancer patient population. Subjects rate items 1 - 28 on a four-point scale (1 = "not at all" to 4 = "very much") with higher score indicating worse functioning/symptoms and the items 29 - 30 on 1 - 7 points scale. It is composed of global health status/QoL scale; five functional scales (physical, role, emotional, cognitive, and social); three symptom scales (fatigue, nausea and vomiting, and pain); and six single items (dyspnea, insomnia, appetite loss, constipation, diarrhea, and financial difficulties).

The following endpoints based on this measure will be analyzed:

- Change from baseline in Global Health Status, Physical Functioning, Cognitive Functioning, Role Functioning

HRQoL assessments per QLQ-BN20 questionnaire developed by EORTC:

Quality of Life Questionnaire Brain Cancer module (QLQ-BN20) is a 20-item patient self-report questionnaire is specifically developed for brain cancer patients. Subjects rate items on a four-point scale (1 = "not at all" to 4 = "very much") with higher score indicating worse symptoms. It is composed of 11 symptom scales (7 single item scales and 4 multi-item scales).

The following endpoints based on this measure will be analyzed:

- Change from baseline in symptom scales of Visual Disorder, Motor Dysfunction and Communication Disorder

MDASI-BT symptom severity score

Details of MDASI-BT symptom severity score are provided in Section 5.3.2. The following exploratory endpoints will be analyzed:

- Change from baseline in neurologic domain score (mean over seizures, numbness, pain, and weakness)
- Change from baseline in cognitive domain score (mean over difficulty understanding, difficulty remembering, difficulty speaking, and difficulty concentrating)
- Change from baseline in treatment domain score (mean over dry mouth, drowsiness, and appetite)

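### SAP 5.3.2 calls the MDASI-BT scores averages, but its formulas give 22 and 6 times the average, and its event lines name a decrease where an increase is deterioration

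*SAP*

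**What the plan says.** SAP Section 5.3.2 introduces the instrument as 22 symptom items and 6 interference items, each rated 0 to 10, "with higher score indicating worse symptoms/interference". The score is given in words: "MDASI-BT symptom severity score is defined as average over 13 core symptom items and 9 brain tumor symptom items". The interference score is likewise an average, over its 6 items.

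The section then sets a completeness rule (at least 12 of 22 items, or 4 of 6). It says the scores, when enough items "are completed on a given assessment using the formula", equal the sum of the answered items multiplied by "22/number of items answered" for severity and by "6/number of items answered" for interference.

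The threshold that follows is a change of at least 1 "point on a 10-point scale at follow-up assessment with respect to baseline will be considered as clinically relevant". A change of −1 or lower is classed as improved, and +1 or higher as deteriorated. The two Deterioration Free Survival endpoints are then listed, and both describe the event as "decrease by 1 unit or death, whichever comes first".

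Other places that bear on the scoring:

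- Protocol Section 14.6.2 computes both scores by averaging, with deterioration at +1 or more. It also refers scoring to the MDASI user manual, as does Protocol Section 14.7.
- SAP Section 5.3.3 defines the MDASI-BT domain scores as plain means. The neurologic domain, for example, is the "mean over seizures, numbness, pain, and weakness".
- SAP Section 10.1.2 leaves PRO imputation to the scoring manuals. SAP Appendix III is titled as the MDASI-BT scoring manual but prints only the questionnaire.
- SAP Section 5.6.2 places the two endpoints fifth and sixth in the fixed testing sequence.

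**The concern.** There are two separate faults.

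The first is arithmetic. An average of 0–10 items and a prorated total of those items cannot both be the score. The 1-point threshold makes sense only on the average. Applied to the printed formula, it flags changes far smaller than the plan regards as clinically relevant. As printed, the total scores would also be on a different scale from their own domain scores.

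The second is direction. A one-unit decrease is an improvement under the section's own coding, so the endpoint lines as printed count improvement as an event. SAP Section 10.1.1 reads a hazard ratio below 1 as benefit. For the non-death events, that reading would be reversed.

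SAP Section 4.0 says the document is there to guide programming, and a formula and an event line are what a programmer implements. At stake is whether the reported time-to-deterioration results for two secondary endpoints mean what their labels say.

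**Working it through.** **Inputs** (all from SAP Section 5.3.2): items scored 0–10; k = 22 severity items or 6 interference items; minimum answered 12 of 22 or 4 of 6; cut-off 1 point on a 10-point scale.

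**The plan's own figures.** The smallest whole number above half of 22 is 12, and above half of 6 is 4. Both completeness figures reproduce.

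**What the printed formula returns.** With n items answered and sum S:

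- Average = S / n.
- Printed score = S × k / n = k × average, for any n.

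With every item scored 3, the average is 3.0. The printed severity score is 66 whether 12 or 22 items are answered, and the printed interference score is 18 whether 4 or 6 are answered. The maxima are 22 × 10 = 220 and 6 × 10 = 60. No passage divides the result by 22 or 6 afterwards.

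**What the 1-point cut-off means on each scale**

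| | Severity (k = 22) | Interference (k = 6) |
|---|---|---|
| Printed cut-off, in points of the average | 1/22 = 0.045 | 1/6 = 0.167 |
| Net item-points for +1 on the average, all answered | 22 | 6 |
| Net item-points for +1 on the printed score, all answered | 1 | 1 |
| One item up by 1, minimum answered at both visits: printed change | 22/12 = 1.83 | 6/4 = 1.50 |
| Same change on the average | 1/12 = 0.083 | 1/4 = 0.25 |

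**Sensitivity to a skipped item.** Suppose all items are answered at baseline with total T. At follow-up one item scored 0 is left blank and no other answer changes.

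- Severity: T × 22/21 − T = T/21, which reaches 1 when T ≥ 21 (average 21/22 = 0.95).
- Interference: T × 6/5 − T = T/5, which reaches 1 when T ≥ 5 (average 5/6 = 0.83).
- At a severity total of 44 (average 2.0), the printed score rises by 44/21 = 2.1. The average rises by 44/21 − 44/22 = 0.095.

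A blank answer alone could therefore meet the printed criterion at that visit. SAP Section 10.1.1 then requires that the criterion still be met at any further assessment within 8 weeks.

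**Direction, side by side.** SAP Section 5.3.2 says higher is worse, −1 or lower is improved and +1 or higher is deteriorated. Protocol Section 14.6.2 has the same categories. Both endpoint lines in SAP Section 5.3.2 say decrease. A decrease is correct for HVLT-R, which is defined directly below them and where a lower recall score is worse. It is not correct for MDASI-BT.

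**What does not change.** The ANCOVA change-from-baseline analyses of the two scores (SAP Section 10.4.7) multiply outcome and baseline by the same constant. The treatment estimate and its standard error scale together, so the p-value stays the same. In one simulated data set it was 0.8926 with multipliers 1, 6 and 22. Only the reported units change.

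**The case against.** The strongest reply is that the intent is clear and literal programming is not certain. The section uses the word average, ties the threshold to a 10-point scale that cannot describe 0–220 or 0–60, and agrees with Protocol Section 14.6.2. The formula may be a step for missing items with the final division left out. The protocol also refers scoring to a user manual that is not reproduced in these documents. This stands in part: the figures of 0.045 and 0.167 apply only if the formula is programmed as printed and the cut-off is applied to its result, and the documents do not show what was programmed. None of it, however, corrects the formula that the SAP prints.

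On direction, SAP Section 10.1.1 defines an event as meeting the deterioration criteria, and the itemised categories give those criteria as an increase. That supports reading the endpoint lines as a drafting slip. The slip occurs in both lines, though, and they still state the opposite of the categories.

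On importance, Protocol Section 1.0 reports an interim OS hazard ratio of 1.01 with one-sided p = 0.628, so formal testing does not reach these endpoints. That stands and limits the consequence. SAP Section 5.6.2 still plans between-arm tests of all endpoints at the interim and final analyses, and SAP Section 5.5.1 includes secondary results in the IDMC's interim review.

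**Conclusion.** The concern holds on both counts. The printed formulas equal exactly 22 and 6 times the score that the same section defines, and both event lines run against its coding of deterioration.

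If programmed as printed, the formulas set the deterioration criterion at 1/22 or 1/6 of the stated change. The event lines would count improvement as deterioration. That conditional is the only assumption; the ratios are exact.

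Reach is limited. The OS and PFS analyses and the overall type I error are not affected. The data and statistics for the seventh to ninth endpoints are also untouched, although in the fixed sequence a misdefined fifth or sixth endpoint could wrongly open or close the way to them. Because OS failed at the interim, that route is moot, and what remains is the correctness of the descriptive results for these two endpoints. This should be fixed, but it does not threaten the trial's main conclusion.

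**What to change.** In SAP Section 5.3.2:

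- Replace both formulas with the sum of items answered divided by the number of items answered, keeping the 12-of-22 and 4-of-6 completeness rules. The score then runs 0–10 for any permitted number of answers, and the 1-point cut-off means what the plan says.
- In both endpoint lines, replace the one-unit decrease with an increase of at least 1 point from baseline.

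Before either endpoint is reported, check the derivation program for the divisor and the direction of the event.

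The cost is two formulas, two endpoint lines and one program check. No new data are needed.

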5.3.3 Exploratory Efficacy Endpoints

Overall Survival (OS)

- Survival rates at the end of 0.5, 1, 2, 2.5, 3, 4, and 5 years
- OS in non-EGFRvIII subjects

Progression Free Survival (PFS)

- Centrally-assessed PFS rates at the end of 0.5, 1, 2, 2.5, 3, 4, and 5 years

- Centrally-assessed PFS for the MGMT unmethylated and methylated sub-groups
- Centrally-assessed PFS in non-EGFRvIII subjects
- Progression free survival (PFS), assessed by investigator

HRQoL assessments per QLQ-C30 questionnaire developed by EORTC:

The Quality of Life Questionnaire Core 30 (QLQ-C30) is a 30-item patient self-report questionnaire validated for use in a cancer patient population. Subjects rate items 1 - 28 on a four-point scale (1 = "not at all" to 4 = "very much") with higher score indicating worse functioning/symptoms and the items 29 - 30 on 1 - 7 points scale. It is composed of global health status/QoL scale; five functional scales (physical, role, emotional, cognitive, and social); three symptom scales (fatigue, nausea and vomiting, and pain); and six single items (dyspnea, insomnia, appetite loss, constipation, diarrhea, and financial difficulties).

The following endpoints based on this measure will be analyzed:

- Change from baseline in Global Health Status, Physical Functioning, Cognitive Functioning, Role Functioning

HRQoL assessments per QLQ-BN20 questionnaire developed by EORTC:

Quality of Life Questionnaire Brain Cancer module (QLQ-BN20) is a 20-item patient self-report questionnaire is specifically developed for brain cancer patients. Subjects rate items on a four-point scale (1 = "not at all" to 4 = "very much") with higher score indicating worse symptoms. It is composed of 11 symptom scales (7 single item scales and 4 multi-item scales).

The following endpoints based on this measure will be analyzed:

- Change from baseline in symptom scales of Visual Disorder, Motor Dysfunction and Communication Disorder

MDASI-BT symptom severity score

Details of MDASI-BT symptom severity score are provided in Section 5.3.2. The following exploratory endpoints will be analyzed:

- Change from baseline in neurologic domain score (mean over seizures, numbness, pain, and weakness)
- Change from baseline in cognitive domain score (mean over difficulty understanding, difficulty remembering, difficulty speaking, and difficulty concentrating)
- Change from baseline in treatment domain score (mean over dry mouth, drowsiness, and appetite)
- Change from baseline in Vision item score (one of the 9 brain tumor-specific items)

MDASI-BT symptom interference score

Details of MDASI-BT symptom interference score is provided in Section 5.3.2. The following exploratory endpoints will be analyzed:

- Change from baseline in activity-related interference domain score (mean over general activity, work, and walking)
- Change from baseline in mood-related interference domain score (mean over mood, relations with other people, and enjoyment of life)

Karnofsky Performance Status (KPS):

- Change from baseline in KPS score
- Median time for which KPS score was maintained at 70 or higher

COWA-FAS verbal fluency

This standardized neurocognitive function test is used to assess change in executive function over time. In this test, patients are asked to name words beginning with F, A and

S in English (and frequency matched letters in other languages). The COWA-FAS verbal fluency score will be computed by summing the total number of unique words.

At each post-baseline assessment, change in raw and standardized COWA-FAS verbal fluency score relative to baseline will be calculated and categorized as deteriorated or not using the reliable change index (RCI) criterion based on the standardized scores. The details are provided in Appendix VII.

The endpoints based on this measure are as follows:

- Deterioration free survival in verbal fluency score
- Change from baseline in verbal fluency score

Neurocognitive functioning based on HVLTR

Details of HVLTR score is provided in Section 5.3.2. In addition to Total Recall Score (over Trials 1 - 3), the following two scores will also be evaluated:

- Delayed Recall Score (Trial 4) and
- Recognition Discrimination Index (= total number of true positives – total number of false positives)

The following exploratory endpoints will be analyzed:

- Change from baseline in Total Recall score
- Change from baseline in Delayed Recall Score
- Change from baseline in Recognition Discriminant Index

EQ-5D-5L Health Index and EQ-VAS

EuroQol 5 Dimensions 5 levels (EQ-5D-5L) is a validated instrument to measure generic health status. It is a 5-item patient self-report questionnaire. Subjects rate items on a five-point scale (1 = "no problems" to 5 = "extreme problem") with higher score indicating worse health. The EQ-5D-5L health states, defined by the EQ-5D-5L

descriptive system, will be converted into a single preference-weighted health utility index score by applying country-specific weights. If country is not available in the look-up table, then weights based on the United States will be applied. Scores will be computed according to procedures outlined in EQ-5D-5L scoring manual, available at https://euroqol.org/wp-content/uploads/2016/09/EQ-5D-5L_UserGuide_2015.pdf.

In the assessment of EuroQol Visual Analog Scale (EQ VAS), subjects are asked to indicate their overall health status on a 0 to 100 visual analogue scale with endpoints labelled 'the best health you can imagine' and 'the worst health you can imagine.' This information is used as a quantitative measure of health as judged by the individual respondents.

The endpoints based on this measure are as follows:

- Change from baseline in EQ-5D-5L index value
- Change from baseline in EQ VAS score.

Change from baseline in corticosteroid dosing

Average daily corticosteroid dose (dexamethasone equivalent) at baseline is defined as any use of systemic steroid within 14 days prior to randomization. Post-baseline steroid use is defined as any use of systemic steroid on or after randomization. Steroid doses will be converted to a dexamethasone equivalent dose.³

Corticosteroids (mg)	Conversion Factor*
Cortisone	0.75/25
Hydrocortisone	0.75/20
Methylprednisolone	0.75/4
Prednisolone	0.75/5
Prednisone	0.75/5
Triamcinolone	0.75/4
Betamethasone	0.75/0.6

* Dexamethasone equivalent dose (mg) = Conversion factor × Corticosteroid dose (mg).

Baseline steroid dose is defined as the average dose within 14 days prior to randomization. Post-baseline steroid dose is defined as average dose from randomization to last dosing of study drug + 49 days.

The endpoint based on this measure is as follows:

- Change from baseline in average daily (dexamethasone equivalent) corticosteroid dosing during treatment period.

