10.5 Sensitivity Analyses

Sensitivity analyses will be conducted to evaluate the robustness of efficacy results. PFS and OS will be analyzed in the PPS using the same statistical methodology.

The primary endpoint of OS will be analyzed based on a stratified log-rank test, adjusting for the study for the study stratification factors.

Two sensitivity analyses will be carried out for PFS endpoint by implementing different censoring rules in the definition of PFS (i.e., modified PFS endpoint). These sensitivity analyses will be conducted in the FAS population using the same statistical methodology as that for the PFS endpoint described in Section [10.3](#).

Sensitivity analysis 1: PFS as time from randomization to the date of progression of disease (PD) assessed centrally per RANO criteria or death, whichever occurs first. Subjects without an event will be right-censored at the date of last follow up for disease progression.

Sensitivity analysis 2: PFS as time from randomization to the date of progression of disease (PD) assessed centrally per RANO criteria or death, whichever occurs first. Subjects with 2 or more consecutive missed assessments (i.e., > 20 weeks since last RANO assessment) without any subsequent assessment prior to the PFS event (i.e., progression or death) will be considered progressed at the planned date of the earliest missed RANO assessment (i.e., last scan date prior to event + 8 weeks). Subjects without an event will be right-censored at the date of last follow up for disease progression.

As a sensitivity analysis, at each post-baseline assessment, change in standardized HVLTR total recall score relative to baseline will be calculated and categorized as deteriorated or not using the reliable change index (RCI) criterion based on the raw scores. The details are provided in Appendix I. Deterioration free survival in HVLTR total recall score (using the RCI criterion) will be analyzed using the stratified log-rank test.

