13.0 Appendix

Appendix I: Determining deterioration in HVLt-R Total Recall score and COWA FAS score

Raw Score will be standardized using the published age-specific normative data from a healthy population as follows.

$$\text{Z score} = \frac{\text{Raw Score} - \text{Mean norm Score}}{\text{Norm standard deviation}}$$

At each post-baseline assessment, change in raw score relative to baseline will be calculated and categorized as declined or not using the reliable change index (RCI) criterion based on the raw scores. The RCI is derived from the standard error of measurement of each test and represents the 90% confidence interval for the difference in raw score from baseline to the next assessment that would be expected if no real change occurred.^{2,14}

$$\text{RCI} = 1.64(\text{SEdiff}), \text{ where } \text{SEdiff} = [2(\text{SEM}^2)]^{1/2} \text{ and } \text{SEM} = \text{SD}[(1 - r)^{1/2}]$$

SEdiff is the standard error of difference, SEM is the standard error of measurement, SD is the standard deviation, and r is the test-retest reliability statistic. All RCI thresholds were rounded to the nearest whole number. For HVLt-R total score and COWA-FAS score, $r = 0.74$ and 0.70 will be used, respectively.⁴ Deterioration in raw score should be compared against the RCI threshold to determine the meaningful deterioration.

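### The SAP gives conflicting scales (raw and standardized) for the reliable-change rule behind exploratory COWA-FAS deterioration and the HVLT-R sensitivity analysis

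*SAP*

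**What the plan says.** **COWA-FAS.** SAP 5.3.3 has change computed on both the raw and the standardized verbal fluency score, and then classifies deterioration "using the reliable change index (RCI) criterion based on the standardized scores". It adds: "The details are provided in Appendix VII". Appendix VII is an empty word-list form with columns for F, A and S words and contains no rule.

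**Appendix I.** Its title covers both HVLT-R Total Recall and COWA-FAS. It first defines a z score, but then states the rule on the raw scale: "change in raw score relative to baseline will be calculated and categorized as declined or not using the reliable change index (RCI) criterion", the criterion being raw-score based. The index "represents the 90% confidence interval for the difference in raw score from baseline to the next assessment", and the appendix closes: "Deterioration in raw score should be compared against the RCI threshold to determine the meaningful deterioration". It also says: "All RCI thresholds were rounded to the nearest whole number". It gives reliabilities of 0.74 (HVLT-R) and 0.70 (COWA-FAS), but no SD and no numerical threshold for either test.

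**HVLT-R sensitivity analysis.** SAP 10.5 takes change in the standardized Total Recall score and has it "categorized as deteriorated or not using the reliable change index (RCI) criterion based on the raw scores", with details in Appendix I. Protocol 14.6.2 also bases the HVLT-R reliable-change criterion on raw scores.

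**HVLT-R secondary endpoint.** SAP 5.3.2 uses a fixed change of 5 raw points. The reliable change index plays no part in it.

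**The concern.** These sentences define events. SAP 5.3.3 and Appendix I put the COWA-FAS rule on different scales, and the reference that should settle the matter leads to a page with no rule. SAP 10.5 mixes two units within one sentence.

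What counts as a decline therefore depends on which sentence is programmed. A standardized change judged against a threshold in raw points would leave an endpoint made up almost entirely of deaths, because SAP 10.1.1 counts death as an event. The HVLT-R sensitivity analysis could then say nothing about whether the 5-point rule gives a robust answer on verbal memory. A standardized COWA-FAS change judged against a threshold rounded to a whole number would err the other way and admit more declines that are only measurement error.

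**Working it through.** **Inputs**
- SAP Appendix I: SEM = SD × √(1 − r); SEdiff = √(2 × SEM²); RCI = 1.64 × SEdiff; r = 0.74 (HVLT-R) and 0.70 (COWA-FAS).
- SD: no figure is given. On the standardized scale I take SD = 1, as protocol 14.6.2 describes for standardized scores. On the raw scale I assume SD 3 to 6 for HVLT-R and 8 to 14 for COWA-FAS.
- Model: with no real change, the difference is normal with SD equal to SEdiff. The false-decline rate at one assessment is Φ(−threshold / SEdiff).

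**1. The plan's own figure.** 2Φ(1.64) − 1 = 89.9%, which agrees with the stated 90%. The lower tail, the false-decline rate, is 5.05%.

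**2. COWA-FAS on the standardized scale (SAP 5.3.3).**
- SEM = √0.30 = 0.548; SEdiff = √0.60 = 0.7746; RCI = 1.64 × 0.7746 = 1.270.
- Not rounded: false decline 5.05%.
- Rounded to 1: 1 / 0.7746 = 1.291 and Φ(−1.291) = 9.84%. That is 1.95 times the unrounded rate, and coverage falls from 90% to 80.3%.

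**3. Persistence.** SAP 10.1.1 requires that the decline not reverse within 8 weeks. With one confirming assessment, and correlation 0.5 between two changes that share a baseline, the COWA-FAS rate is 1.24% unrounded and 3.16% rounded. A decline with no assessment in the next 8 weeks still counts unconfirmed, so step 2 applies to it.

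**4. Raw change against a raw threshold (Appendix I).**
- Continuous normal model, threshold rounded: COWA-FAS 4.7% to 5.3%, HVLT-R 3.2% to 6.2% over the assumed SDs. Rounding moves the rate either way.
- Whole-word counts with a continuity correction: COWA-FAS is 5.3% to 6.3% with rounding and 4.5% to 5.7% without, still a small effect. HVLT-R is more sensitive, because one word is a larger share of its threshold. At an assumed SD of 3.5 the RCI is 4.14; a cut-off of 4 words gives 8.3%, and the next whole count above 4.14, 5 words, gives 3.7%. This is a reason to print the threshold.

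**5. SAP 10.5 taken literally (HVLT-R).**
- Raw RCI = 1.64 × √0.52 × SD = 1.183 × SD. SD 3 gives 3.55, rounded to 4; SD 6 gives 7.10, rounded to 7.
- Standardized SEdiff = √0.52 = 0.7211. A standardized change set against 4 lies 4 / 0.7211 = 5.55 standard errors out, so false decline is below 0.001%.
- In words, if the same SD is used to standardize, a subject would have to lose 4 × 3 = 12 words at SD 3 or 7 × 6 = 42 words at SD 6. SAP 5.3.2 regards 5 as clinically relevant. Almost no true decline would qualify.

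**The case against.** The best reply is that Appendix I settles the matter. It names both tests in its title, holds the only formula, and says raw three times. Any programmer must use it to compute an index at all. The rounding sentence stands in that raw-score text, and both tests count whole words, so rounding a standardized threshold is something no sentence directs. On this view the defects are a stray word in 5.3.3, another in 10.5 and a wrong appendix number.

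Much of that stands. The 9.84% arises only if 5.3.3 is joined to a rounding rule written for raw scores, and Appendix I is probably what was meant. But 5.3.3 is the section that defines the endpoint, it names the other scale explicitly, and it does not point to Appendix I. SAP 10.5 does point there and still takes change on the standardized scale. Appendix I alone also yields no threshold, because it gives no SD.

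Three stronger readings are tempting, and the documents do not support them:
- **That rounding doubles false declines for both tests.** Nothing bases the HVLT-R criterion on standardized scores; SAP 10.5, Appendix I and protocol 14.6.2 all say raw. Even on the standardized scale the HVLT-R index of 1.18 rounded to 1 would give 8.28% against 5.05%, or 1.64 times.
- **That the tested HVLT-R endpoint is compromised.** Its rule is the fixed 5-point raw change.
- **That the comparison between arms is biased or type I error inflated.** The threshold is the same in both arms, and SAP 10.1 tests exploratory endpoints at a nominal level without adjustment. No differential effect is shown.

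**Conclusion.** The inconsistency is real and sits in the operative rules, but its reach is limited to exploratory COWA-FAS deterioration-free survival and the HVLT-R sensitivity analysis. The primary endpoint and the secondary testing sequence are untouched.

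The firmest part needs only a modest assumption. With a raw threshold of about 4 points or more, which the formula gives for any raw SD of 3 or above, the literal rule in 10.5 reduces the HVLT-R sensitivity analysis to little more than an analysis of deaths. The COWA-FAS inflation, 5.05% to 9.84% per assessment, is conditional on joining 5.3.3 to the rounding sentence. It rests on the normal model with SD = 1, and the persistence rule lowers the absolute rates. With raw scores throughout, rounding matters little for COWA-FAS. The priority is low, but the wording should be corrected because as written it can produce a wrong event definition.

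**What to change.** 1. In SAP 5.3.3, base the COWA-FAS criterion on raw-score change against the raw-score RCI, and change the reference from Appendix VII to Appendix I.
2. In SAP 10.5, replace change in the standardized HVLT-R score with change in the raw score.
3. In Appendix I, state the SD and its source for each test, and print the resulting numerical threshold.
4. In Appendix I, say that whole-number rounding applies to raw-score thresholds only. If a standardized version is kept anywhere, leave its threshold unrounded.

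The cost is a few sentences in three places. It needs no new data and no change to the tested endpoints or the sample size. If results have already been produced, the study report should state which scale and which numerical threshold were programmed for each test.
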